OFFICIAL STUDY TITLE: HIGH FLOW OXYGEN THERAPY VERSUS CONVENTIONAL OXYGEN THERAPY IN CARDIAC SURGERY PATIENTS- OPTICAR STUDY

PROTOCOL SUBMITTED FOR IRB APPROVAL: Evaggelismos General Hospital, Athens, Greece, Date: March 3, 2017 [Protocol ID: NKU ATHENS; OPTICAR 47/03/2017]

ClinicalTrials.gov Identifier: NCT03282552

High Flow Oxygen therapy versus Conventional Oxygen Therapy in Cardiac Surgery Patients-OPTICAR study

Applying Investigators

1. **[name], MSc, PhD(c), Cardiothoracic Intensive Care**
2. **[name], PhD, Consultant in Intensive Care Medicine**
3. **[name], PhD, Professor in Intensive Care Medicine**
4. **[name], PhD, Lead Consultant in Cardiac Surgery**
5. **[name], PhD, Associate Professor in Intensive Care Medicine**

Brief summary

High flow oxygen therapy has been applied after extubation in cardiac surgery patients with uncertain efficacy. The current authors plan to conduct a prospective, randomized, controlled study of nasal high flow therapy (NHF) application with higher (60 L/min) or lower flow (40 L/min) oxygen mixture administration versus standard oxygen treatment (Venturi mask) after extubation of patients undergoing elective or non-elective cardiac surgery.

Detailed description

Over the past decade, nasal high flow (NHF) has been introduced for oxygen therapy in adults. Its indications have been expanded, especially in cases of acute hypoxic respiratory failure.

The device consists of an air/oxygen blender connected via an active heated humidifier to a nasal cannula, through a single limb, heated inspiratory circuit. It delivers a fraction of inspired oxygen (FiO₂) from 21% to 100% with a flow rate up to 60 L/min. FiO₂ adjustments are independent of the set flow rate so that the patient is given heated, humidified high-flow oxygen, with a flow that can be adjusted above the patient's maximum inspiratory flow rate, thereby increasing confidence about the actual FiO₂ being delivered to the patient.¹ These device characteristics make it more promising in comparison with conventional low- and high-flow oxygen devices (e.g., nasal cannula, non-rebreathing masks, Venturi masks), especially in patients with high inspiratory flow rates, such as patients with acute respiratory failure (ARF).^{1,2}

The benefits arising from application of oxygen with high flow rates via NHF are 1) reduction in the entrainment of room air and thus ensuring higher and more stable FiO₂ values,^{3,4} 2) generation of positive airway pressures during expiration as a result of the expiratory resistance imposed to the patient's exhalation against the continuous high flow of incoming oxygen gas,⁵⁻⁸ 3) improving mucociliary function and clearance of secretion by continuous heating and humidifying of the administered gas,^{9,10} 4) reducing dead space ventilation^{11,12} and 5) reducing work of breathing¹³.

All the aforementioned NHF mechanisms of actions exert various effects on the respiratory system, including improved gas exchange, lower respiratory rate and effort and improved lung mechanics which are correlated with more comfort and less subjective dyspnea.¹³⁻¹⁵

Respiratory complications after cardiac surgery can affect morbidity and mortality, and increase the healthcare cost.^{16,17} Advanced age, duration of extracorporeal circulation, history of significant underlying cardiac or pulmonary disease and phrenic nerve injury are the main

prognostic factors for post cardiac surgery respiratory complications.^{18,19} Traditionally, low- and high-flow oxygen systems are used to reverse postsurgical respiratory complications with or without addition of continuous (CPAP) or bi-level (NIV) positive airway pressure.²⁰⁻²² NHF might be superior for the prevention or treatment of those respiratory complications, since it can provide high-flow of heated and hydrated oxygen while the positive airway pressure created by the high gas flow can recruit alveoli and increase the end-expiratory lung volume.^{23,24}

Studies applying NHF immediately after extubation in cardiac surgery patients revealed better oxygenation and less need for advanced methods of respiratory support compared to conventional oxygen devices^{25,26}, and similar results compared to noninvasive ventilation²⁷. However, Zochios et al,²⁸ summarized all the available up to date data of NHF compared to conventional oxygen devices and non-invasive ventilation in patients undergoing cardiothoracic surgery and they did not find any further benefit by NHF use. The aforementioned discordant results could be explained by the differences in the studied populations and NHF flow settings. The proposed initial flow rate differs among the studies, with some authors^{2,4} suggesting initial lower flows (35-40 L/min) that will be better tolerated by the patients and others suggesting initial maximal flows (60 L/min) to rapidly relieve dyspnea and prevent muscle fatigue.^{29,30}

Aim

The primary goal of the study is to evaluate the efficacy of NHF versus conventional oxygen systems as regards treatment failure (as defined below) and respiratory parameters [respiratory rate, PaO_2 / (fraction of inspired oxygen) FiO_2 , peripheral oxygen saturation (SpO_2), use of accessory muscles, and dyspnea and comfort as regards the technique of respiratory support by using a visual analogue scale (VAS) after the extubation of cardiac surgery patients. An additional major goal of the study is to compare two different initial NHF flows of 60 L/min and 40 L/min, intensive care unit (ICU) Length of Stay, Hospital Length of Stay, rates of ICU re-admission and re-intubation and any other respiratory / non-respiratory complications and adverse events. The rate of failure of the initial treatment will be determined as the primary study outcome.

Methods

This is a prospective, non-blinded, randomized study in post-extubated cardiac surgery patients. The study population will consist of three patient groups: The first group (Study Group 1) will include patients on NHF with initial settings of $\text{FiO}_2=0.6$ and gas flow=60L/min. The second group (Study Group 2) will include patients on NHF with initial settings of $\text{FiO}_2=0.6$ and gas flow=40L/min. In the third group (control group) all patients will receive oxygen therapy according to the standard practice of our cardiac ICU department, i.e., Venturi mask with $\text{FiO}_2=0.6$ and flow of 15 L/min.

Treatment failure will be defined as any crossover from one treatment to another due to patient's respiratory distress and discomfort. To be more specific, switch of gas flow from 40L/min to 60L/min, crossover from either NHF group to standard practice (Venturi mask) or need for more advanced respiratory support such as non-invasive ventilation or invasive mechanical ventilation, inability to reverse FiO_2 and/or gas flow escalation above initial settings within 48 hours of its initiation. Escalation reversal will be defined as return to initial (or lower) FiO_2 and/or gas flow for ≥ 4 hours.

Inclusion criteria will be: Cardiac ICU adult patients > 18 years after elective or urgent cardiac surgery having passed a successful Spontaneous Breathing Trial (SBT) with T-piece and $\text{FiO}_2=0.6$. A successful SBT will have to fulfil the following criteria^{31, 32, 33} respiratory rate: 12-29 breaths/min, $\text{SpO}_2 > 92\%$, $\text{PaCO}_2 < 45\text{ mmHg}$, heart rate <120/min, and systolic arterial pressure of 90-160 mmHg while receiving norepinephrine at a rate of 0.00 $\mu\text{g}/\text{kg}/\text{min}$ to 0.15 $\mu\text{g}/\text{kg}/\text{min}$. The most important inclusion criterion is residual respiratory impairment at the end of SBT defined as $\text{PaO}_2/\text{FiO}_2 < 200 \text{ mmHg}$ while receiving $\text{FiO}_2=0.6$. The decision to extubate under these specific conditions will be made by the attending physicians.

The exclusion criteria will comprise: 1) Obstructive Sleep Apnea Syndrome supported by a continuous positive airways pressure device, 2) preoperative diagnosis of Chronic Obstructive Pulmonary disease, 3) patients already tracheostomized, 4) do not resuscitate status, 5) Glasgow Coma Scale score <13, 6) Insufficient knowledge of Greek Language , and 7) any visual or hearing impairment.

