Patients will be assessed for gradual reduction in the intensity of respiratory support or need for support escalation every 4 hours postextubation. Gradual weaning from NHF will be accomplished by FiO₂ decrease to 0.5, followed by gas flow decrease to 30 L/min NHF weaning target will include an FiO₂ of 0.4 and a gas flow of 20 L/min.^{8,42} If at an NHF FiO₂ of 0.4 and a flow rate of 20 L/min, SpO₂ can be maintained at >92% and respiratory rate remains within 12-20 breaths/min for ≥ 2 hours, patients will be switched to a Venturi mask providing an FiO₂ of 0.4). In the Control group, a reduction of FiO₂ to 0.4 (via a Venturi mask) will be sought. Patients of all groups fulfilling the aforementioned SpO₂/respiratory rate criteria for at least 4 hours while receiving an FiO₂ of 0.4 via a Venturi mask will be considered for ICU discharge. As part of standard practice, patients will be scheduled for twice-daily physiotherapy.

Regarding treatment escalation in Study groups, if SpO₂ drops to $\leq 92\%$ for at least 5 min at a gas flow of less than 60 L/min, gas flow will first be increased by 5-10 L/min.⁴ Next, if SpO₂ remains at or below 92%, FiO₂ will be increased⁴³ to achieve an SpO₂ of >92%. In the Control group, an SpO₂ of 92% or less for at least 5 min will be initially treated with FiO₂ increase. In all groups, persistent and/or worsening hypoxemia will be ultimately treated with non-invasive mechanical ventilation and/or reintubation and initiation of invasive mechanical ventilation.

Treatment decisions and premature discontinuation of physiological data collection

Changes in the intensity and/or modality of respiratory support will ultimately be decided by the primary attending physicians of the patients. Initiation of mechanical ventilation or ICU discharge within 48 hours of extubation will result in discontinuation of the pre-specified 4-hourly patient data collection.

Outcome measures

Primary: Occurrence of treatment failure; regarding the NHF groups, this will be further specified as inability of weaning from NHF (i.e. inability of achieving successful weaning from NHF) according to study protocol.

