‡, In SG 2, support escalation should be initially accomplished by gas flow increase of 5-10 L/min; this can be followed by FiO₂ titration to an SpO₂ of more than 92%.

[figure not shown]
§, Regarding CG patients on nonrebreathing mask due to respiratory support escalation, an FiO₂ reduction from 0.9 to 0.6 via a Venturi mask should be performed for escalation reversal.

**, Reversal of respiratory support escalation is defined as return to initial (or lower) FiO₂ and/or gas flow for at least 4 hours.

Applicable definition of hypoxemia: SpO₂ drop to 92% or less for at least 5 min.

SOP FOR THE RATING OF THE LEVEL OF BREATHING COMFORT

At the specified time points of patient follow-up: Investigators should use the below-displayed comfort/discomfort visual analogue scale to help patients rate the level of their breathing comfort. The following simple question should be asked: How would you rate the level of your breathing comfort starting from 0 (maximum discomfort – feeling unable to breathe) to 10 (maximum comfort – feeling capable of smooth and steady breathing, without having even the slightest difficulty).

Contents

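### The primary outcome is not scored by one rule across arms: a reversed rise from 40 to 60 L/min can be scored either way, and the weaning clause names only the NHF groups

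*Combined protocol and SAP*

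**What the plan says.** **Methods, definition of treatment failure.** Failure is introduced as a crossover between treatments because of respiratory distress and discomfort. The items then listed include a "switch of gas flow from 40L/min to 60L/min", a move from NHF to the Venturi mask, a need for non-invasive or invasive ventilation, and inability to reverse FiO2 "and/or gas flow escalation above initial settings within 48 hours of its initiation". The next sentence reads "Escalation reversal will be defined as return to initial (or lower") FiO2 and/or flow, held for at least 4 hours. The notes to the SOP diagram repeat this reversal rule without exception.

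**Management of respiratory support.** In the Study groups, when SpO2 is 92% or less for at least 5 minutes at a flow below 60 L/min, "gas flow will first be increased by 5-10 L/min"; FiO2 follows if SpO2 stays low. In Control, the same SpO2 finding "for at least 5 min will be initially treated with" more FiO2. The SOP diagram note for Study group 2 agrees: "support escalation should be initially accomplished by gas flow increase of 5-10 L/min". The Detailed description gives a device "with a flow rate up to 60 L/min", which is Study group 1's starting flow.

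**Outcome measures, Primary.** The outcome is treatment failure; "regarding the NHF groups, this will be further specified as inability of weaning from NHF".

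**Statistical Analysis Plan.** The group effect on treatment failure is assessed by multivariable Cox regression. Scheduled data collection runs to 48 hours after extubation (Patient monitoring and data collection).

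**The concern.** A composite outcome supports a randomized comparison only if the same clinical course is scored the same way in every arm. Three features work against that here.

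- The switch clause can apply only to Study group 2. Beside it stands a reversal clause that also covers flow escalation above initial settings, and the two give opposite scores for the same patient.
- The weaning clause applies only to the two NHF groups. It has no deadline, and the text does not say whether it adds to the Methods definition or replaces it.
- Cox regression needs a date for each event. Non-reversal and non-weaning are failures to achieve something, and no date is assigned to either.

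Comparing 60 with 40 L/min is a stated major goal (Aim), and few failures are expected in those arms. The trial is non-blinded, so a rule left open could be settled with the arm known.

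**Working it through.** **1. One course scored under both clauses.** Each row is a patient whose support rises above the initial setting, returns to it for at least 4 hours within the window, and who has no other event.

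| Arm | Rise | Switch clause | Reversal clause |
|---|---|---|---|
| Study group 1 | FiO2 (flow already at the 60 maximum) | cannot apply | not failure |
| Study group 2 | flow, 40 to 60 L/min | failure | not failure |
| Control | FiO2 | cannot apply | not failure |

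Only the Study group 2 row conflicts. If any listed item suffices, that patient fails while the other two do not. If the reversal rule governs, none fails. A rise from 40 to 60 needs 20/10 = 2 to 20/5 = 4 increments. The text does not say whether a gradual rise counts as a switch.

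**2. Weaning clause.** Control has a goal of Venturi FiO2 0.4, but missing it is not called failure. If the clause adds to the Methods definition, it can only add NHF failures. If it replaces that definition for NHF, the direction is uncertain: an NHF patient with an unreversed escalation who later weans would not fail, while a comparable Control patient would.

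**3. The plan's own figure.** Inputs from Sample Size and Power Analysis: 10%, 20%, 51%; alpha 0.05; equal groups. For a three-group chi-square test with 2 df, the mean rate is 0.27 and w² = mean[(p − 0.27)²]/(0.27 × 0.73) = 0.1546, so w = 0.393. With noncentrality N·w², N = 63 gives power 0.804, and N = 99 gives 0.948 against the stated 0.96. The plan's 63 is reproduced, so the sample size is not in dispute.

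**4. Tipping count, flow comparison.** Planned gap: 33 × (0.20 − 0.10) = 3.3 patients. With a common censoring time, HR ≈ ln(1 − p2)/ln(1 − p1), so the planned HR is ln 0.80/ln 0.90 = 2.12. Start from no difference (3/33 in each arm) and score m reversed switchers as failures in Study group 2:

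| m | Study group 2 | HR |
|---|---|---|
| 1 | 4/33 | 1.36 |
| 2 | 5/33 | 1.72 |
| 3 | 6/33 | 2.11 |
| 4 | 7/33 | 2.50 |

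Three such patients (9% of the arm) reproduce the planned effect. A single result of 6/33 versus 3/33 is not significant (Fisher p = 0.48).

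**5. Rejection rates under assumed switcher rates.** Simulation: 33 versus 33, exponential times censored at 48 hours, unadjusted log-rank (Cox score) test, 20,000 runs, true failure 10% in both arms. The alpha of 0.05/3 assumes three Bonferroni comparisons.

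| Reversed switchers scored as failures (assumed) | P(p < 0.05) | P(p < 0.05/3) |
|---|---|---|
| 0% | 0.05 | 0.01 |
| 10% of Study group 2 | 0.21 | 0.09 |
| 20% of Study group 2 | 0.55 | 0.35 |

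With Fisher's exact test, which the plan names for percentages, the 10% case is about 0.12 rather than 0.21.

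**6. NHF versus Control, same method.** With 66 versus 33 and Control at 51%, NHF failure of 15%, 20% and 25% gives power 0.97, 0.90 and 0.76. The last two rates assume the weaning clause adds 5 or 10 points. The Cox covariates are not simulated in steps 5 and 6.

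**7. Reversal window.** If the 48 hours run from the escalation, the share inside scheduled collection is (48 − t)/48 for an escalation begun t hours after extubation: 75%, 50% and 25% at t = 12, 24 and 36.

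**The case against.** The best defence is that the Methods definition is coherent as a list of alternatives. Its lead-in speaks of crossover for distress, and moving from 40 to 60 L/min means taking up the other NHF arm's flow. The reversal clause would then cover FiO2 rises and flow rises short of 60. The Aim makes failure of the initial treatment the primary outcome, and a patient started at 40 who needs 60 may be just that. The planned 20% for Study group 2 may already include such patients. This is a legitimate intention, but the visible text does not state it, does not exempt the switch from the reversal rule, and does not use the reason for the change to separate the two items; one patient can have both reasons. Even on this reading, a reversed rise to 60 fails while a reversed FiO2 rise elsewhere does not.

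Some stronger inferences are not supported:

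- *That the titration rule carries Study group 2 to 60.* The written sequence is a flow increase of 5-10 L/min and then FiO2. Repeated flow steps are allowed, not prescribed.
- *That Study group 1 always escalates by FiO2.* Once weaned below 60 L/min, it also escalates by flow first. The asymmetry concerns only rises above initial settings.
- *That the reversal window overruns data collection.* This depends on what the word initiation refers to. If it is the start of treatment, the window closes with the 48-hour collection. The 4-hourly support assessments also have no stated 48-hour end.

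The SOP diagram is not visible in the available text, only its notes, and it may settle part of this. The notes do include a Control reversal step, from a nonrebreathing mask back to the Venturi mask.

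**Conclusion.** The point holds. The visible text contains a switch clause that only one arm can meet, in conflict with the reversal rule beside it, and a weaning clause that names only the NHF groups. Event times for non-reversal and non-weaning are undefined.

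A reader might infer that the flow comparison is biased against 40 L/min. That follows only if reversed switches are scored as failures and are not intended as failure of the initial treatment; the documents settle neither. A reader might also infer that the trial's main comparison is unsafe. The figures do not show that: NHF versus Control keeps power of 0.90 or 0.76 under the assumed added failures, and an additive weaning clause would work against NHF, not in its favour. Ventilation and unreversed escalation are written for all arms and remain comparable, provided the weaning clause does not replace them for NHF.

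The true size is unknown. The switcher and weaning-failure rates above are assumptions, used only to show that about three patients are enough to match the whole planned difference between flows.

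**What to change.** Change the scoring only, not care.

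1. Reconcile the Methods definition, Management of respiratory support, Outcome measures and the SOP diagram notes into one failure definition, with the same components and the same reversal rule in every arm. Fix it before arm-level data are examined.
2. Within it, state whether a gradual rise to 60 L/min counts as a switch or as an escalation, and which clause prevails.
3. Report NHF weaning failure as a separate secondary outcome, or apply an equivalent clause to Control. Either way, give it a deadline.
4. For the Cox model, define the event time of each component, say from when the 48-hour reversal window runs, and state how escalations still open at 48 hours are handled.
5. Tabulate components by arm, and report the flow comparison with the 40-to-60 switch scored both ways.

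The cost is revised wording, one table and one sensitivity analysis. Failure rates may depart from the planned 10%, 20% and 51% in either direction, and support settings may need recording past 48 hours for patients with an open escalation.

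### The general rule and the specific list for treatment failure disagree on a 60-to-40 L/min change, so the two NHF arms can be scored differently on the primary outcome

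*Combined protocol and SAP*

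**What the plan says.** Three statements in the combined protocol and SAP define the primary outcome.

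- Methods, general sentence: "Treatment failure will be defined as any crossover from one treatment to another due to patient's respiratory distress and discomfort". No direction is given.
- Methods, the list offered straight afterwards as the more specific version: "switch of gas flow from 40L/min to 60L/min, crossover from either NHF group to standard practice (Venturi mask"; then "need for more advanced respiratory support such as non-invasive ventilation or invasive mechanical ventilation"; then "inability to reverse FiO_2 and/or gas flow escalation above initial settings within 48 hours of its initiation". A change from 60 to 40 L/min is not named, nor is a change from Venturi mask to NHF.
- Outcome measures, primary: "regarding the NHF groups, this will be further specified as inability of weaning from NHF", according to the protocol.

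Three other places bear on how these work.

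- The Detailed description reports some authors "suggesting initial lower flows (35-40 L/min) that will be better tolerated by the patients", and describes the device as one "with a flow rate up to 60 L/min".
- Management of respiratory support makes a flow reduction part of weaning: "Gradual weaning from NHF will be accomplished by FiO₂ decrease to 0.5, followed by gas flow decrease to 30 L/min".
- The trial is not blinded, and the attending physicians have the final decision on changes of support.

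**The concern.** The only flow switch on the list is upward. Study group 1 starts at the device maximum, so as a move away from the assigned starting flow this item can arise only in Study group 2. The corresponding problem at 60 L/min is that the patient cannot tolerate the flow and is moved down to the other arm's starting flow. The protocol's own background points to this drawback, yet the list is silent on it, and the last list item counts only changes above the initial settings. If the patient is later weaned, the wording in Outcome measures also gives a non-failure.

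Two scorers could therefore classify the same patient differently on the primary outcome, depending on which statement they apply. At stake is mainly the comparison of the two starting flows, which the Aim section ranks as a further major goal. Because the treating team knows the allocation and decides the changes, the scoring rule should not be left to interpretation.

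**Working it through.** **1. The statements side by side.** Each row is a change made because of distress or discomfort.

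| Change | General sentence | List | Weaning wording (NHF arms) |
|---|---|---|---|
| Study group 2, 40 to 60 L/min | failure | failure, named | depends on later weaning |
| Study group 1, 60 to 40 L/min, later weaned | failure on a literal reading | no item applies | not a failure |
| Either NHF arm to Venturi | failure | failure, named | unclear, since weaning also ends on a Venturi mask |
| Control to NHF | failure on a literal reading | only if NHF counts as more advanced support | does not apply |

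The second row is the conflict. The third row shows that the plan already needs the reason for a change to tell failure from weaning.

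**2. The plan's own figures.** Sample Size and Power Analysis gives failure rates of 10% (Study group 1), 20% (Study group 2), 15% pooled and 51% (control), with alpha 0.05, 63 patients for power 0.80 and 99 for power 0.96. Allocation is 1:1:1, P values are two-tailed, and percentages are compared by Fisher's exact test. Exact power is the sum, over all pairs of failure counts (i, j), of Bin(i; n1, p1) x Bin(j; n2, p2) wherever the two-sided Fisher P is at most 0.05.

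- 42 NHF vs 21 control, 15% vs 51%: 0.817 (stated 0.80).
- 66 NHF vs 33 control, 15% vs 51%: 0.952 (stated 0.96).

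The stated figures reproduce to within 2 points as a pooled 2:1 comparison, so there is no arithmetic error here.

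**3. Expected failures by flow arm.** 33 x 0.10 = 3.3 and 33 x 0.20 = 6.6. The whole predicted difference is 3.3 patients.

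**4. Sensitivity.** The documents give no rate of intolerance-driven 60-to-40 changes. Let x be the assumed share of Study group 1 with such a change who do not fail otherwise, and suppose the planned 10% does not already include them. If they are counted, the Study group 1 rate is 0.10 + x, the gap (Study group 2 minus Study group 1) is 0.20 - (0.10 + x) = 0.10 - x, and the pooled NHF rate is (0.30 + x)/2.

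| x (assumed) | Extra failures (33x) | Study group 1 | Gap, points | Pooled NHF | Power, pooled NHF vs control (66 vs 33, Fisher) |
|---|---|---|---|---|---|
| 0 | 0 | 10% | +10 | 15% | 0.952 |
| 5% | 1.65 | 15% | +5 | 17.5% | 0.913 |
| 10% | 3.3 | 20% | 0 | 20% | 0.858 |
| 15% | 4.95 | 25% | -5 | 22.5% | 0.787 |
| 20% | 6.6 | 30% | -10 | 25% | 0.700 |

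By the same Fisher calculation, the 60 versus 40 L/min comparison at 10% versus 20% with 33 per arm has power of only 0.115. These are powers for comparing proportions, not for the planned Cox model.

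**The case against.** The strongest reply is that the general sentence already covers the case. It has no direction, and since the list treats a 40-to-60 change as a crossover, a 60-to-40 change can be one too. This stands in part. A reader might infer that the plan excludes 60-to-40 changes outright, and the documents do not support that. But the list is presented as the more specific statement, nothing says whether it is exhaustive, and the joint wording about distress and discomfort leaves pure intolerance of the flow unclear.

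Second, a flow cut is not automatically weaning progress. FiO2 is to come down to 0.5 before flow, so a cut made at FiO2 0.6 is out of order and could be identified if settings are recorded. Being weaned also requires more than one cut: FiO2 0.4 and 20 L/min with the saturation and respiratory-rate criteria met for at least 2 hours, or the earlier physician-decided switch that the later protocol summary allows. All this is true. However, no scoring rule uses that order, and a cut for intolerance after FiO2 has reached 0.5 looks the same as a weaning step.

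Third, intolerance is not lost. It is recorded among the adverse events, tolerance on the VAS is a secondary outcome, and leaving NHF for a Venturi mask because of discomfort is a listed failure. That is correct, but the adverse-event record and the VAS do not enter the primary outcome.

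Fourth, the study forms and the procedural diagram are not in the available text and may already capture the reason for each change. This cannot be settled from the documents.

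Finally, a reader might add the control-to-NHF omission to the same tilt. It does not belong there. NHF may fall under the open-ended item on more advanced support, it is not a step in the described control pathway, and if such rescues went uncounted the error would favour control.

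**Conclusion.** The concern holds as a conflict between the general sentence, the list and the weaning wording. Scoring by the list and the weaning wording treats mirror-image changes in the two NHF arms differently and would tilt the 60 versus 40 L/min comparison towards 60 L/min. It would be going too far to call that bias established, because scoring by the general sentence removes it.

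The size is conditional. About three patients in Study group 1 equal the whole predicted difference between the flow arms, and the range of +10 to -10 points rests entirely on an assumed 0 to 20%, on those patients not failing otherwise, and on the planned 10% excluding them. The flow comparison has little power in any case, so a few scoring decisions could outweigh the true difference. Pooled NHF versus control, which the sample size fits, is less exposed: power is still about 0.86 at an assumed 10%, although it falls to 0.70 at 20%. The point should be fixed, but it does not undermine the trial's main contrast.

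**What to change.** Reconcile the general sentence and list in Methods with the primary outcome wording in Outcome measures, and say whether the list is exhaustive. Make scoring symmetric: any change to another arm's device or starting flow made because of distress or discomfort is scored the same way in every direction, including 60 to 40 L/min and Venturi to NHF, and is kept distinct from a protocol weaning step. Base that distinction on the recorded reason, because the readable text sets explicit criteria for leaving NHF but not clearly for an earlier flow reduction.

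Record the reason for each flow or device change, if the study forms do not already do so. Add a sensitivity analysis of the primary outcome with intolerance-driven 60-to-40 changes counted and not counted.

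This alters outcome scoring only, not how patients are managed. The cost is some wording, slightly more recording, one extra analysis, and possibly a less favourable failure rate in the 60 L/min arm.
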